Objectives: We will examine the feasibility of a novel, multifaceted, home-based prehabilitation intervention designed to improve functional capacity and postoperative outcomes for frail Veterans anticipating cardiothoracic surgery. Specific aims are to:

- (1) Estimate rates of recruitment, retention, and adherence to the intervention; and evaluate participation barriers.
- (2) Measure changes over time in frailty, physical function, pulmonary function, nutrition, and health-related quality of life at baseline, the day of surgery, and 30 and 90 days after surgery.
- (3) Explore changes in postoperative mortality, major complications, length of hospital stay, and level of independent living using case-matched historical controls.

**Methods:** This single-arm pilot study will enroll a consecutive cohort of up to 50 Veterans identified as frail using a standardized frailty assessment and scheduled for major cardiothoracic surgery at the VA Pittsburgh Healthcare System. The 4 week long prehabilitation regimen will include: (a) aerobic conditioning, (b) strength and coordination training, (c) respiratory muscle training, and (d) nutritional coaching and supplementation. Pre- and post-prehabilitation assessments will include: (a) frailty; (b) physical function; (c) pulmonary function; (d) nutrition; and (e) health-related quality of life. Postoperative outcomes will include length of stay, mortality

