#### Research Procedures/Interventions:

**C.1. Overview.** In this single-arm pilot study, we will enroll a consecutive cohort of up to 50 Veterans identified as frail using a standardized frailty assessment and scheduled for major cardiothoracic surgery at the VA Pittsburgh Healthcare System. The 3-6 week long prehabilitation regimen will include: (a) aerobic conditioning, (b) strength and coordination training, (c) respiratory muscle training, and (d) nutritional coaching and supplementation. Pre- and post-prehabilitation assessments will include: (a) frailty; (b) physical function; (c) pulmonary function; (d) nutrition; and (e) health-related quality of life. Using physical performance tests, biomarkers, chart review, survey instruments, and patient logs, we will assess the feasibility of the recruitment, randomization, retention and assessment procedures, compensating patients for their time. Prehabilitation will not last more than 4 weeks for CABG patients. However, for non-cardiac thoracic patients, prehabilitation may be extended out to 6 weeks if the surgeon and patient so choose.

**C.2. Eligibility criteria.** We will recruit frail patients (i.e., RAI $\geq$ 16 and Physician /Provider request for patient with RAI<16) scheduled for a CABG or Valve Surgery. Major non-cardiac thoracic surgery is defined according to VA Surgical Quality Improvement Program (VASQIP) criteria that include cases requiring general, epidural, or spinal anesthesia. It includes 193 unique CPT codes ranked by complexity (26 standard, 146 intermediate, and 21 complex) and excludes 58 low risk “minor” surgical procedures with limited morbidity (e.g., bronchoscopy, percutaneous lung biopsy). From these major surgeries, we will include those procedures that deliberately violate the visceral or parietal pleura with something larger than an 18 gauge needle. For example, we will include lung and esophagus resections of all kinds, but exclude thoracentesis. Exclusion criteria are designed to ensure participant safety in prehabilitation exercises (e.g., low-risk, stable cardiac disease without significant symptoms, arrhythmias, hemodynamic instability or critical coronary lesions). Based on historical data, we expect 2/3rds of eligible

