patients to exhibit mild frailty (RAI 16-25) with essentially intact independence and capacity for prehabilitation. Higher degrees of frailty may impose barriers to full participation, but characterizing those limitations is an important component of this pilot. We will stratify enrollment to ensure approximately equal enrollment of cardiac and non-cardiac thoracic patients.

**C.3. Prehabilitation procedures.** Prehabilitation will last 3-6 weeks—a time frame that does not delay surgery, corresponds to the typical lag for surgical scheduling, and strikes a pragmatic balance between improving physiologic reserve without unduly delaying definitive surgical therapy. Although the training intervention is only 3-6 weeks, studies repeatedly demonstrate neuromuscular strengthening, diminished inflammation, and respiratory improvements within this time. Further, the program also fosters continuity between preoperative training and traditional postoperative rehabilitation, facilitating rapid mobilization and progressive exercise after surgery. Strategies like this enhance functional recovery and reduce the risks of subsequent episodes of disability (e.g., readmission or loss of independence). If clinical contexts such as neoadjuvant chemotherapy or worsening angina require shorter (or permit longer) durations of training, we will examine these events in order to inform the optimal duration of prehabilitation for a larger clinical trial.

**(a) Safety.** Prehabilitation will begin in a telemetry-monitored, hospital-based setting to train patients in the home-based exercises and establish safe targets of exertion. If and as safety is established, exercise will shift to the home with weekly telephone/ VA Video Connect contact to ensure safety and reinforce technique. Remote telephone and VA Video Connect monitoring will be enhanced by the relationships, familiarity, and trust established during the hospital-based sessions. Although safety concerns will require some patients to complete all exercise in monitored, hospital-based settings, we anticipate that many patients will safely transition to home-based exercise after 1-4 hospital-based sessions. Study staff will initiate withdrawal procedures for patients who demonstrate insufficient cognitive or physical capacity to safely carry out the prescribed activities.

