**C.4. Assessment Schedule (Table1).** As shown in Table 1, research staff will collect baseline data, including demographics, living location, physical performance, and nutrition, at the time of recruitment. Assessments will continue every 2 weeks up to and including the day of surgery, and then postoperatively at 30 and 90 days. Even among the robust, physical performance deteriorates immediately after surgery, but returns to baseline by 90 days. Among the frail, the deterioration may endure, increasing the severity of frailty. Physical Performance Tests will be administered by exercise physiologists in the VAPHS Rehabilitation facility, located near the IMPACT clinic, and thus convenient for patients. Nutrition Assessments include serum prealbumin and c-reactive protein collected each time the participation is onsite for an assessment by a hospital phlebotomists, and the 7-point SGA administered by hospital nutritionists at baseline and again on the day of surgery. Patient Logs will assess patient adherence with the prehabilitation regimen and document progress. Family members or

other caregivers can assist patients in completing the log books if needed. Survey Instruments will be administered either face to face, by telephone/ VA Video Connect, or by mail, depending on patient preference. Responses will be entered directly into REDCap using a project utility distinct from the RAI measurement tool. For patients electing surveys by mail, we will send printed copies of the Redcap forms with a self-addressed, stamped envelope for return. Responses on returned surveys will be keyed into Redcap before storing the paper surveys in locked cabinets. Chart reviews will be completed by research staff to determine details of the surgical procedure, postoperative mortality, length of stay, and major complications. Patient Interviews will be conducted to evaluate barriers to prehabilitation and explore possible solutions. We will also track the time required to complete each measure to inform the design of the subsequent multi-center trial.

Assessments will end after the assessment planned for 90 days after the surgery. Ideally, patients will return to the hospital for this final visit to conduct measures of physical performance and nutrition along with the survey instruments. However, if they are unable to make the visit, we will conduct the surveys over the phone.

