**Table 1: Assessment Schedule**

	Baseline	Every other Week In-hospital	Day of surgery	30 Days post-op	90 Days post-op
Demographics					
Age, sex, race, ethnicity, etc	X				
Procedure-related variables	X			X	
Living Location	X		X	X	X
Physical Performance					
SPPB	X	X	X		x
MIP & MEP	X	X	X		x
6 Minute Walk Test	X	X	X		X
Frailty (multiple measures)	X	X	X		x
Nutrition					
Prealbumin (biweekly)	X	X	X		x
BMI	X	X	X		x
Subjective Global Assessment	X		X		x
Compliance					
Patient Logs		X	X		
Barrier Assessment	X	X	X	X	X
Outcomes					
Mortality				X	X
Length of Stay				X	
Major Complications (30 day)				X	
Quality of Life	X		X		X
Quality of Surgical Care (Pre)			X		
Quality of Surgical Care (Post)				X	
Measure of Flourishing	X		X		X
Measures of Decision Quality	x		x	X	x

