- Quality of Surgical Care will be measured with the Surgical Care Survey (SCS) that includes subscales for quality of pre-surgical care (11 items), day of surgery (6 items), and postoperative care (12 items).
- Flourishing will be measured by the “Secure Flourish” measure, which is 12 items assessing 6 domains: happiness & life satisfaction, mental & physical health, meaning & purpose, character & virtue, close social relationships, and financial & material stability. All items are scored from 0 to 10. This measure is calculating by summing the scores of all six domains.[96]
- Measures of Decision Quality include Decision Regret (5 items), Patient Centeredness of Care (12 items), Satisfaction with the Process of Decision Making (14 items), Satisfaction with the IMPACT clinic (8 items), Satisfaction with the frailty diagnosis (8 items), satisfaction with the palliative care consult (8 items), and Satisfaction with the surgeon (8 items).
- Mortality. Patients completing the 30- and 90-day surveys will be confirmed alive. For all others, chart review including telephone contact with identified surrogates will confirm vital status and date of death (if deceased).
- Length of Stay will be calculated from the date of surgery to the date of discharge or transfer from the hospital. We will also record the time spent in the intensive care unit. Intervals will be calculated in days.
- Major Complications will be abstracted from the chart according to VASQIP coding rules (Appendix). The presence or absence of each complication will be recorded separately, but analysis will focus on a dichotomous outcome indicating the occurrence of serious, Clavien-Dindo level IV complications. These include deep wound infections, organ space infections, wound disruption, pneumonia, unplanned intubation, pulmonary embolism, mechanical ventilation for >48 hours, progressive renal insufficiency, acute renal failure, stroke, coma, cardiac arrest, myocardial infarction, bleeding in excess of 4 units, deep vein thrombosis, sepsis and C. difficile colitis. This approach to analyzing complications has been shown to correlate with frailty. Co-I and Chief of Surgery [name] has authorized the VASQIP nurse abstractor to use standard VASQIP procedures to code the charts of participating patients.

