**(c) Ascertain the feasibility of measuring changes over time in frailty, physical function, pulmonary function, nutrition, and health-related quality of life at baseline, the day of surgery, and 30 and 90 days after surgery [Aim 2].** We will summarize the time required to complete each assessment as well as the completeness of data, estimating completion rates with CIs. Graphical analyses will assess simple changes in frailty, physical performance, pulmonary function, nutrition and quality of life over the study period. Although sample size will limit model fit, we will prepare analyses for the larger trial by developing simple mixed models to explore changes over time (baseline and every other week up to the day of surgery, and then 30 and 90 days after). Separate models for each outcome will assess changes, including a fixed effect for time and a random effect for subject. The type of mixed model will depend on the outcome variable with linear mixed models for continuous variables (e.g., RAI, SPPB, 6MWT, MIP, MEP, etc) and generalized mixed models for ordinal/categorical variables (e.g., SGA, frailty phenotype). We will also explore dose-response relationships based on the actual duration of and adherence to the training regimen.

**(d) Explore changes in postoperative mortality, major complications, length of hospital stay, and level of independent living using case-matched historical controls [Exploratory Aim].** We will match each participant to an historical control using local VASQIP data. VASQIP data include variables sufficient to calculate the RAI as well as details about the patient's procedure, comorbidities, outcomes, and a highly reliable prediction of postoperative 30-day mortality. Each historical control will be chosen from VAPHS VASQIP data from the 2 years prior to the study start and matched to the enrolled participant based on procedure, age, RAI score, and VASQIP predicted mortality. We will summarize separately the total number of deaths and major complications at 30 and 90 days for all patients, estimating proportions with associated CIs for the intervention and historical control groups. We will also compute summary statistics (mean, median, standard deviation, range) for length of hospital stay and return to independent living. We will then attempt to assess if differences exist between the groups with regard to these post-operative measures.

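### Deaths and complications are counted only from surgery, so harm or a lost operation during the training weeks shows at most as unexplained non-retention

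*Combined protocol and SAP*

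**What the plan says.** The study is a single-arm pilot. Under C.1, "we will enroll a consecutive cohort of up to 50 Veterans identified as frail". The intervention comes before the operation: "Prehabilitation will last 3-6 weeks" (C.3).

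The event outcomes start at the operation.

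- **Aim (Objectives and C.8(d)).** "Explore changes in postoperative mortality, major complications, length of hospital stay, and level of independent living using case-matched historical controls".
- **Analysis (C.8(d)).** "We will summarize separately the total number of deaths and major complications at 30 and 90 days for all patients". Each participant is matched to a local VASQIP control on procedure, age, RAI and predicted mortality.
- **Schedule (Table 1).** Mortality is marked at 30 and 90 days after surgery. The complications row, whose label begins "Major Complications (30 day", is marked at 30 days after surgery. Neither is marked at baseline, at the every-other-week visits or on the day of surgery.
- **Definitions (C.5).** Stay runs from the date of surgery. On mortality, "Patients completing the 30- and 90-day surveys will be confirmed alive"; for everyone else, vital status and date of death come from the chart and from surrogates.

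C.3 foresees clinical events during training, but gives a limited reason for looking at those that change its length: "worsening angina require shorter (or permit longer) durations of training, we will examine these events in order to inform the optimal duration". It also describes telemetry, monitored sessions and withdrawal of patients who cannot exercise safely. C.8 plans no tabulation of such events.

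**The concern.** The period in which the intervention could do harm lies before the clock starts. C.5 lists myocardial infarction and cardiac arrest among the major complications. An infarction after surgery is counted; the same event in the third training week has no scheduled field and no analysis. A participant who dies or whose operation is cancelled has no postoperative day 30 or 90, and C.8(d) does not say how that person enters the denominator.

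The controls come from a surgical database and are matched on procedure, so they were presumably all operated. The comparison then asks how patients fare once they reach surgery. It cannot show whether training affected the chance of reaching it. The brief description says the findings will inform a larger randomized trial, whose designers will want to know how many frail patients got to surgery without a serious event.

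**Working it through.** The plan derives no sample size and states no event rate, so there is no figure to reproduce. The counting window is settled by reading; the arithmetic below only illustrates it.

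**Where a preoperative event would appear**

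| Event before surgery | Mortality, complications, stay | Aim 1 retention |
|---|---|---|
| Death | No postoperative time point | Not retained, cause not shown |
| Surgery cancelled | No postoperative time point | Not retained if postoperative procedures are not completed, cause not shown |
| Infarction survived, then operated | Postoperative course counted; the infarction is not | Can count as retained |
| Surgery brought forward | Postoperative course counted; the reason is not | Can count as retained |

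**Illustration**

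Inputs: 50 enrolled (the ceiling in C.1). Assumed: 2 postoperative deaths, and all other unoperated participants alive at the cut-off. The numbers of preoperative deaths (k) and other unoperated participants (c) are also assumed.

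- Surgery-anchored mortality = 2/(50 − k − c)
- Enrolment-anchored mortality = (2 + k)/50
- Maximum retention = (50 − k − c − 2)/50
- Intervals are exact (Clopper-Pearson) 95%

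| k | c | From surgery | From enrolment | Maximum retention |
|---|---|---|---|---|
| 0 | 0 | 2/50 = 4.0% (0.5-13.7) | 2/50 = 4.0% (0.5-13.7) | 48/50 = 96% |
| 2 | 5 | 2/43 = 4.7% (0.6-15.8) | 4/50 = 8.0% (2.2-19.2) | 41/50 = 82% |
| 0 | 10 | 2/40 = 5.0% (0.6-16.9) | 2/50 = 4.0% (0.5-13.7) | 38/50 = 76% |
| 5 | 5 | 2/40 = 5.0% (0.6-16.9) | 7/50 = 14.0% (5.8-26.7) | 38/50 = 76% |

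The last two rows carry the point. Surgery-anchored mortality and retention are identical, yet one cohort had no preoperative deaths and the other had five.

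The last row also shows that the wording on all patients leaves the denominator open. The same data give 2/40 = 5.0% (operated only), 2/50 = 4.0% (all enrolled, postoperative deaths only) or 7/50 = 14.0% (all enrolled, all deaths).

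**Chance that the gap matters**

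If the preoperative risk of death or a serious event is p, the chance of at least one among 50 is 1 − (1 − p)^50. For assumed p of 1%, 2% and 5% this is 40%, 64% and 92%.

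**Limit of any count**

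With 0/50, the two-sided 95% upper limit is 1 − 0.025^(1/50) = 7.1%.

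**The case against.** The preoperative weeks are not unmeasured. Aim 1 estimates, with confidence intervals, the proportion retained through the 90-day procedures, and a preoperative death or lost operation lowers it. Date of death is sought for everyone who does not complete the surveys. C.5 records the procedure codes of both the planned and the performed operation. Physical performance, frailty and nutrition measures start at baseline, with most repeated at the every-other-week visits: "Assessments will continue every 2 weeks up to and including the day of surgery, and then postoperatively at 30 and 90 days". Barrier interviews cover difficulty with retention and adherence. The comparison is labelled exploratory, and C.8 makes feasibility its focus. Controls also had to reach surgery, so conditioning on surgery affects both sides, and the direction of any net bias is not established. All of this stands.

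It rules out three stronger readings that a reader might infer:

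- *Preoperative harm enters no outcome at all.* It can enter retention. What is missing is the cause.
- *Every clinical outcome starts at surgery.* Only mortality, major complications and stay do.
- *The programme is made to look safe by design.* The plan states no safety objective and draws no safety conclusion. Adverse-event reporting may sit outside the text supplied, so its absence from the study as a whole cannot be asserted.

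None of this closes the gap in C.8. Retention cannot separate a death from a withdrawal or a missed final visit, and collecting a date of death does not define an analysis of it.

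**Conclusion.** The point holds for the mortality, complication and stay summaries. As written, they describe patients from the operation onward, and C.8 counts no events for the training weeks. The matched comparison is conditional on reaching surgery; this rests on the inference, from the VASQIP source and the matching on procedure, that all controls were operated.

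The size is unknown because the documents give no event rates. Under the assumed counts, mortality from enrolment could be 4.0% or 14.0% with the same surgery-anchored rate (5.0%) and the same maximum retention (76%). The share of calendar time spent in training does not measure bias and is not used here.

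The gap is mainly one of analysis and denominators. It does not undermine the retention estimate or the functional measures, but it should be closed before the results inform a larger trial.

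**What to change.** 1. **C.8(b).** Report, with exact confidence intervals, among all enrolled and separately among those who start training, the number who die, have a serious event, or have surgery cancelled or brought forward, with the reason. Serious events should include at least the VASQIP-listed ones, such as myocardial infarction or cardiac arrest, and unplanned admission. Count from enrolment to surgery, or to a stated fixed day if there is no operation.
2. **C.5 and Table 1.** Add these items for the preoperative period, with definitions.
3. **C.8(d).** State that the matched comparison covers operated participants only, give that denominator, and show preoperative deaths and cancellations beside it. In the same edit, reconcile the complication time points: C.8(d) names 30 and 90 days, Table 1 only 30.

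Much of the source is already planned: date of death, planned and performed procedure codes, chart review and weekly calls. The planned chart review is aimed at the operation and its aftermath, however, so preoperative events need added fields, definitions and some abstraction time, and unoperated participants need follow-up to the fixed day. The safety picture may look less favourable. With at most 50 patients the count is descriptive and cannot establish safety.

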Minimizing the Burden of Assessments: Some participants in this study will be concurrently enrolled in a related study of frailty and preoperative palliative care consultation (Pro1840). Some of the outcome assessments planned for Pro 1840 are identical to those planned here. When a participant is enrolled in both studies (Pro1840 and Pro 2192) the study coordinators will work together to ensure that participants do not have to complete identical assessments twice. At any given time point when potentially duplicative assessments could occur, study staff will record the participant's singular response to a duplicative question simultaneously into the case report forms (CRFs) of each separate study. This could be accomplished by having a two separate study staff on the phone or in the room as the patient is interviewed. It could also be accomplished by having a single cross-listed staff member (e.g., listed on the staff form of both studies) administer the assessment and record the responses into the separate CRFs of each study at the same sitting. Additionally, some participants may be concurrently enrolled in a minimal risk study (PI [name] MD; Pro1843) that has similar inclusion criteria. However participation in Pro1843 will not impact the outcomes of this protocol (2192).

To reduce patient burden due to travel once a patient has been determined to be safe to take part in home exercise they will have the option to complete an remote biweekly assessment via VA VideoC onnect. Biweekly Assessments for patients that are unable to make it to the hospital will complete an remote, home-based biweekly assessment while on VA Video Connect with research staff members. VA Video Connect will be used in conjunction with Bluetooth connected peripheral monitors that record and transmit blood pressure, pulse, and oxygen saturation in real time. Single lead cardiac telemetry will also be used once this peripheral is made available (date pending). We will also monitor the patient visually through the video feed to ensure safety. The remote assessment will included the following items form the standard assessment: Five chair rises (standing and siting form a chair 5 times), two 4 meter walks at usual walking speed, assessment of breathing capacity on the threshold trainer (adjusted by RPE scale with goal of RPE 11-13), and if space allows a modified 6 minute walk test.

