- Frailty will be assessed through several measures because no single measure of frailty captures the breadth of the syndrome. In addition to the RAI described above, we will quantify the Hopkins & Edmonton Frail Scales and independently analyze the gait speed and handgrip strength that is part of the Hopkins Frail Scale. We recently developed a streamlined approach to measuring all of these metrics simultaneously in a parsimonious exercise that takes <5 minutes to administer.
- Hopkins Frail Scale encompasses slowness, weakness, weight loss, low physical activity, and exhaustion with  $\geq 3/5$  criteria required to distinguish frailty. It is the most frequently cited tool shown to predict mortality and disability in large cohorts of community-dwelling elders and surgical patients.
- Edmonton Frail Scale is an 11-item survey that assesses 8 dimensions of frailty. Each item is scored 0, 1, or 2 with higher scores indicating greater frailty. The total score ranges from 0-17 with good inter-rater reliability ( $k = 0.77$ ), moderate internal consistency ( $\alpha=0.62$ ), and strong correlation with a geriatrician's assessment of frailty ( $r=.64$ ,  $p<.001$ ).
- Gait speed is one key measure of frailty that has excellent inter-rater reliability (intraclass coefficient 0.88-0.96) and test-retest reliability (intraclass coefficient 0.86-0.91).
- Handgrip Strength has also been demonstrated to have key utility as an index of frailty. A grip dynamometer will be used, averaging 2 serial assessments from the dominant hand.
- Prealbumin will be measured with standard serological testing. Changes can be detected in days, and it is the best available biomarker of nutrition. However, because prealbumin can function as an acute phase reactant, we will also concurrently measure c-reactive protein as a measure of inflammation and interpret prealbumin as proposed by Jensen, et al.
- Body Mass Index (BMI) will be calculated from height and weight assessed each week at the Cardiac Rehab facility, and is considered the most suitable, objective anthropometric indicator of nutritional status, and changes in BMI have been shown to predict survival in the elderly.

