**(e) Additional exploratory analyses.** Two related pilot studies conducted by the PI use methods similar to those described here (e.g., Pro 1840 & Pro 1754). In particular, these studies collect identical patient reported survey measures and identical physical performance measures. Each study describes analyses of these data to generate reliable estimates of central tendency and dispersion for use in designing future studies. And in the case of this study and Pro 1754, they describe measuring change over time during the pre and post operative period. However, each study has struggled with recruitment leading to smaller than expected sample sizes. Therefore, we plan to transfer de-identified data from Pro 1840 and Pro 1754 into this study to augment the sample size and thereby increase the precision and power

of our estimates. We do not plan or expect data analysis of this augmented sample to differ in any way from that described in 1840 and 1754 and to which the participants gave consent; the only difference is that the value of each participant's data is augmented by joining it to other similar data.

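### C.8(e) pools Pro 1840 records to raise the sample size but has no step for people enrolled in both studies, so on shared measures they count twice

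*Combined protocol and SAP*

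**What the plan says.** Two parts of the combined protocol and SAP bear on this, and the plan does not connect them.

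**C.4, Minimizing the Burden of Assessments.** Co-enrolment is expected: "Some participants in this study will be concurrently enrolled in a related study of frailty and preoperative palliative care consultation (Pro1840". The measures overlap: "Some of the outcome assessments planned for Pro 1840 are identical to those planned here". To spare patients, "the study coordinators will work together to ensure that participants do not have to complete identical assessments twice". Staff do this by entering the participant's "singular response to a duplicative question simultaneously into the case report forms (CRFs) of each separate study". For a co-enrolled person, a shared question therefore yields one answer stored in two databases.

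**C.8(e), Additional exploratory analyses.** Because recruitment fell short in each study, "we plan to transfer de-identified data from Pro 1840 and Pro 1754 into this study to augment the sample size", with more precision and power as the stated gain. The reason given for joining the data is that "these studies collect identical patient reported survey measures and identical physical performance measures". The target is estimates of central tendency and dispersion for designing later studies. The section expects the analysis to be no different from that described in the other two protocols and presents the joining of data as the only change.

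No section describes a cross-study identifier, a co-enrolment flag, an exclusion rule or a count of the overlap.

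**The concern.** The second copy of an answer carries no new information, so it cannot deliver the precision for which the data are pooled. If both copies stay in, the record count exceeds the number of people. Any standard error, interval or power figure computed on records as if they were independent is then too favourable. These estimates are meant to feed the design of later studies, so a reader would place more trust in them than the number of patients warrants.

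Timing matters too. The records arrive de-identified, and C.8(e) does not say whether a code survives the transfer. The pairs are easy to mark beforehand, while staff know who is in both studies, and less certain to be recovered afterwards.

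**Working it through.** **The plan's own figure.** There is none to reproduce. The plan gives no pooled n, no overlap, and no interval width or power for the pooled analysis.

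**Inputs**
- Co-enrolment with Pro 1840, and one answer entered in both sets of forms: C.4.
- Three studies pooled, each smaller than expected: C.8(e). C.1 caps this study at 50; the sizes of Pro 1840 and Pro 1754 are not given.
- Assumed: 30 records per study, so N = 90.
- Assumed: k = 3, 6 or 15 people in both this study and Pro 1840, and none shared with Pro 1754.
- Correlation between the two copies, ρ = 1 for a shared question, because it is the same answer.

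**Formulas**
- Unique people: N − k. Overstatement of n: N/(N − k) − 1.
- Variance of the mean with duplicates left in: σ²(N + 2kρ)/N². The naive variance is σ²/N.
- True SE over naive SE: r = √[(N + 2kρ)/N].
- Coverage of a nominal 95% interval: 2Φ(1.96/r) − 1.
- Half-width in SD units: 1.96/√n.
- Expected sample variance over σ²: 1 − 2kρ/[N(N − 1)].

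**Results, N = 90, ρ = 1**

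| | k = 3 | k = 6 | k = 15 |
|---|---|---|---|
| Unique people | 87 | 84 | 75 |
| n overstated by | 90/87 − 1 = 3.4% | 90/84 − 1 = 7.1% | 90/75 − 1 = 20% |
| r | √(96/90) = 1.033 | √(102/90) = 1.065 | √(120/90) = 1.155 |
| Coverage, mean | 94.2% | 93.4% | 91.0% |
| Half-width, 90 records | 0.207 SD | 0.207 SD | 0.207 SD |
| Half-width, unique people | 0.210 SD | 0.214 SD | 0.226 SD |
| Expected variance / σ² | 0.999 | 0.999 | 0.996 |

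The last row shows that the SD is almost untouched. The mean is unbiased if co-enrolled patients resemble the rest.

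**Physical tests.** C.4 documents a single entry for shared questions. For performance tests, a shared measurement is an assumption. If each study measured separately, ρ would be below 1. As a guide, C.5 gives gait speed a "test-retest reliability (intraclass coefficient 0.86-0.91"). At ρ = 0.86 and N = 90, r = √[(90 + 1.72k)/90] = 1.028, 1.056 or 1.134, and coverage is 94.3%, 93.7% or 91.6%. The picture is much the same.

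**Direction.** For any k above zero with positively correlated copies, r exceeds 1, so the naive interval is too narrow whatever the true overlap.

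**The case against.** The strongest reply is that little of what the plan promises is damaged. C.8(e) asks for central tendency and dispersion, and the working shows that both survive almost intact. The plan specifies no interval for a pooled mean or SD; the intervals named elsewhere in C.8 are for proportions. This stands. The coverage figures apply only if such an interval is computed, although the appeal to precision and power suggests some inference. The overstated n needs no such condition.

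A second reply is that the analysis follows two protocols not seen here, that a sensible analyst would remove duplicates, and that identical answers across a multi-item survey would reveal the pairs. All of this is possible. None of it is in this plan, which presents joining as the only change. It does mean that repair after transfer should not be called impossible.

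A reader might also infer more than the documents support:
- **That the Aim 2 mixed models are compromised,** because a model "including a fixed effect for time and a random effect for subject" cannot merge two copies under different IDs. C.8(e) ties change over time to this study and Pro 1754, whereas co-enrolment is documented for Pro 1840. The random effect is not shown to be involved.
- **That Pro 1754 also overlaps.** Nothing says so. C.4 does mention co-enrolment in Pro 1843, but those data are not pooled.
- **That the effect is larger.** Pooling this study with Pro 1840 alone (N = 60, same k) would overstate n by 5%, 11% or 33%, with coverage of 93.8%, 92.6% or 89.0%. The plan pools three studies, so those are not the figures to lead with.
- **That pooled models need source-study terms.** Whether the studies differ in population or intervention is a separate question from counting people twice.

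**Conclusion.** The point holds as a minor one. The plan creates duplicate answers for co-enrolled people, then adds the second study's records to increase n, and gives no step to prevent double counting. Followed as written, it overstates the pooled n on shared measures, and any standard error or interval that treats records as independent is too small.

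The size cannot be fixed from the documents. It rests on the assumed 90 records and 3, 6 or 15 shared people. At 3 the effect is negligible. The largest case needs half of this study and half of Pro 1840 to be co-enrolled, whereas C.4 says only that some participants are. The finding is confined to the exploratory pooled analysis in C.8(e). The Aim 1 rates and the historical-control comparison are not shown to be affected.

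**What to change.** Add to C.8(e) a sentence on how participants in both this study and Pro 1840 are counted. Before de-identification, the coordinators who already handle these participants should do one of two things: assign a common coded ID across the two studies, or drop the Pro 1840 copy of the shared measures. Keep one record per person per time point. Report unique N, the size of the overlap and n by source study beside any pooled estimate.

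The cost is one code list or exclusion list made before transfer, plus the added counts in the tables. The downside is a smaller stated augmented n.
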